We have to do the same to our brain. It has to unlearn the previous learning that dogs are dangerous. In other words, the brain has to learn by experience that its feared object is actually safe by spending safe time with it. That's the basic principle of exposure therapy. We gradually expose a person to what they're afraid of until the brain gradually learns it's

safe and the fear goes away. We also explain that exposure therapies are very effective. By conducting it with AR, we offer our participants the feeling of safety by exposing them to a virtual dog. By means of this technology, our participants will feel a sense of total control in terms of what is going to happen. Even though they will know that the dogs are not real, the brain does not distinguish the experience in terms of learning.

After the briefing, both groups will be given a form of informed consent. After that the baseline measurements with the real dog will be taken. The participants will then be randomly assigned to either control or intervention conditions. Both groups will be informed about their groups, explained the rationale for the random assignment and control group. The control group will only be tested for baseline where the intervention group will receive Augmented Reality Exposure Therapy.

5. Real Dog Exposure to Measure the Baseline

We explain to the patients why we need to measure their progress with the real dog. To have a baseline measure of their phobia, we introduce the dog to the patient. When the patients stand 7 meters away from the real dog we encourage them to walk closer by saying "Is that it or do you think you can approach more?". If they can go closer to the dog, we say "Can you hold your hand close to it? Can you touch it?" When the participants reach the limits of their comfort zone that is they can not approach closer, we ask whether they would like to finish the testing.

The distance participants can approach the dog will be measured in terms of meters, the Behavioral Approach Test (BAT). Any physical contact with the dog will be measured visually for exclusion criteria i.e., the participants who can touch the dog will be excluded from the study based on the reasoning that they do not have a real phobia.

The Skin Conductance Response (SCR) will be measured to see physiological stress of the individuals via Shimmer3 GSR+ device placed on one finger. At the same time, participants will report how stressed they are (subjective unit of distress, SUD).

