Participants will then be randomly assigned to either control or intervention conditions. Both groups will be informed about their groups, explained the rationale for random assignment and control group.

We say "Now you are comfortable with all these dogs, let's see how you will do with the real dog. I'm excited to see how you'll do."

6. Rooms for the Intervention

We will use two rooms for the intervention. Both rooms have enough clear space on the floor to eliminate the risk of obstruction by objects and also to have better render the AR dogs.

The first room for the intervention is bigger than the second room. The rationale for the difference is that we aim to generalize the exposure learning in the first room to broader and different contexts. Thus, we have two different looking rooms of different sizes.

7. The Intervention with the Augmented Reality Headset

a. The First Room

- Patient stands or sits in a corner of the room.
- We place one breed of dog at the furthest corner of the room (We have 3 dog breeds in various sizes we can modify).
- We ask the patients how scared they are out of 10, that is their Subjective Unit of Distress (SUD). Based on their level of fear we go on adjusting (Minimum to continue is 5/10).
- We start with one dog and then we put the other breeds next to it. We keep asking them what their SUDs are. Then we determine which one is the least scary to the patient and proceed with it only.
- We say "It is not going to get close to you, it is just going to move horizontally." Then, we move the dog horizontally a little bit. We keep repeating it until the participants' SUDs go down.
- When SUDs go down, we say "The dog is going to walk towards you a little bit or closer to you a little bit" (We keep repeating that).
- The dog comes to the middle of the room and starts moving horizontally.
- When their SUDs decrease, we add the second dog. Both dogs move horizontally.
- Then the third breed is added and makes the same horizontal movement.
- We then ask the patient to choose a breed of their liking to stay.
- We then say "Let's go walk towards it a little bit." and "Can you go with me?" and we go with the patient whilst monitoring their SUDs.
- We say "Let's stay here" and "Can you sit there?" (during this stage, we talk and joke with the patients to help them relax)
- We then include patients' cognitive processing. We ask the patient to describe the dog. We say for example "Can you tell me where the dog's head and tail are?"

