- We leave the room and talk with the patient via the walky talky.
- We say "I will put these 3 dogs and they are going to move all around you without my prompt."
- We include their cognitive processing and encourage them to describe the dogs by saying "Tell me what the dogs are doing? Tell me how many dogs are you counting? How many of them are moving, how many of them are standing or jumping?"
- When the participants are comfortable with their virtual phobic stimuli (SUD = 2) or their SUD's did not change for the last 10 minutes, we finish the intervention.

Ending

- When it's finished, we say "That is how exposure therapy works."
- We encourage them to try it at home. We say: "Watch videos and look at pictures of dogs. If you see a dog and you know it is safe, try to pet and play with them. If you see a dog on a leash walking with their owner, walk by them. Don't avoid it."
- Finally, we ask them to come back for the next measurement.

8. Follow-Ups

- At 1 week and 1 month follow-ups, we contact the participants and invite them to the lab. We test them using the real dog to confirm if their gains are maintained. We use the same measures and protocol as the 6th step, Real Dog.

9. Statistical Analysis

Data will be analyzed by using a statistical software called IBM SPSS 26.0. Considering the groups as fixed factor, linear mixed models will be used to evaluate the effectiveness of the Augmented Reality Exposure Therapy on the primary (Behavioral Approach Task) and secondary outcome measures (Specific Phobia Scale, Skin Conductance and Subjective Units of Distress).

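### A scripted performance-expectation line that fits only treated participants sits in the baseline real-dog section, tied to no visit or arm, and could cue post-treatment BATs

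*Combined protocol and SAP*

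**What the plan says.** Section 5 describes the baseline real-dog test. It opens with "We explain to the patients why we need to measure their progress with the real dog". Participants start 7 metres away and are prompted to come nearer, ending with "Can you hold your hand close to it? Can you touch it". Approach distance in metres is the BAT. Skin conductance is recorded, and at the same time "participants will report how stressed they are".

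The section then turns to random assignment, after which "Both groups will be informed about their groups". Its last lines are a staff script: "Now you are comfortable with all these dogs", an invitation to "see how you will do with the real dog", and a sentence saying that staff are excited to see the result.

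The AR material comes only after this. Section 6 begins "We will use two rooms for the intervention", and section 7 gives the AR procedure. The part headed Ending closes with "Finally, we ask them to come back for the next measurement" and lists no real-dog test that day. Section 8 names real-dog tests at 1 week and 1 month and says they follow the procedure of the sixth step, labelled Real Dog. Section 4 says that controls are tested at baseline only. Section 9 makes the BAT the primary outcome, with group as the fixed factor.

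**The concern.** The closing script is in the wrong place for what it says. It presumes a finished session with several dogs and a real-dog test about to start. Neither is true at the end of the baseline section, and the first can never be true of a control.

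This matters because the BAT depends on effort, is prompted by staff and is done by participants who know their group. A line that tells someone they are now comfortable, and that staff look forward to their performance, is an expectancy cue. Spoken before a post-AR BAT, it could shorten the approach distance and lower the SUD reported at that test, both in the direction that favours AR. The baseline BAT has no such cue, so part of the measured change could come from the script and not from the treatment.

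The assertion may also be untrue for some participants. Section 7 allows the AR session to end because distress ratings have not moved for 10 minutes, not only because the participant has become comfortable.

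**Working it through.** No figure in the plan can be reproduced here, and no effect size can be computed. The check is one of order and wording.

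**Order in the document.** Baseline BAT (section 5) → randomisation (section 5) → the scripted line (end of section 5) → AR in the first room, then the second (section 7) → request to return (Ending) → real-dog tests at 1 week and 1 month (section 8). The line is printed after the baseline test and before any AR. Only its content, not its position, links it to a coming test.

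**Counts from the text.**
- Scripted approach prompts in section 5: 3 (whether the participant can come closer, hold a hand near the dog, touch it). Prompts that mention AR or expected performance: 0 of 3.
- Sentences in the closing script: 2. The first refers to an earlier session; both refer to the coming performance.
- Post-AR real-dog tests listed: 2 (1 week, 1 month). Same-day post-AR tests listed: 0. Tests the text shows to be preceded by the line: 0.

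**Where section 8 leads.** It sends follow-up testing to step 6, but step 6 is the rooms. The label Real Dog matches only section 5, the one real-dog procedure in the document. Staff who follow section 8 therefore arrive at the section that contains the line. Nothing tells them to omit it, and a treated participant at follow-up is someone to whom it could sensibly be said. This does not prove that it is said, because section 5 also contains randomisation text that cannot be repeated at follow-up.

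**What the line would do under each reading.** Let *c* be the shift in approach that the cue causes.

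| Reading | Treated change from baseline | Between-arm difference |
|---|---|---|
| Leftover text, never spoken | unaffected | unaffected |
| Spoken before an unlisted same-day test | true change + *c* | shifted only if controls have a matching test |
| Spoken at 1 week or 1 month, controls tested at baseline only | true change + *c* | no concurrent control BAT to compare |
| Spoken at 1 week or 1 month, controls also tested then | true change + *c* | true difference + *c* |

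The documents give the 7 m starting distance but no sample size, SD, expected change or cue effect, so *c* has no derivable value.

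**The case against.** The strongest reply is that this is an editing slip. The randomisation paragraph just before the line nearly repeats section 4, and the step number in section 8 is wrong. Both suggest that sections were moved and not tidied, and leftover text biases nothing. This stands as a real possibility, and it is why the harm is stated conditionally. It does not dispose of the point: staff would still have a script with no stated time to use it, in the section to which follow-up testing is sent.

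A reader might infer three stronger things that the documents do not support.

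- *That the plan provides no visit at which the line could be used.* Section 8 names two real-dog tests after AR. What is missing is a same-day test and any link between the line and a visit.
- *That an unlisted same-day test must exist.* Section 5 speaks of progress and section 8 of gains being maintained. Both are compatible with such a test, but gains could equally mean lower SUDs in AR.
- *That the comparison of arms is biased in favour of AR.* The line is assigned to no arm or visit, and section 4 says that controls are tested only at baseline. On that wording there is no later control BAT, and the cue could distort only the treated arm's change. Section 8 refers simply to participants, so control follow-up is not settled either way.

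It is also fair to say that both groups are told before baseline that exposure works very well, that allocation is known to participants and that the approach prompts are themselves encouraging. The line would add to this expectancy, and nothing shows by how much. The difference is that the briefing and the prompts are present at baseline and the line is not.

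Finally, one could object to deleting a line before its purpose is known. If it has a use outside assessment, the sponsor can state where. It is not suitable immediately before a BAT under any reading.

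**Conclusion.** The point holds in a conditional form. It is certain that the line cannot apply at baseline or to an untreated control, that it is tied to no visit or arm, that no same-day post-AR real-dog test is listed, and that the cross-reference in section 8 is wrong and can sensibly mean only the section containing the line.

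It is conditional that any BAT is affected. For the treated arm's change from baseline to be inflated, the line must be spoken before a post-AR BAT and participants must respond to it. For the between-arm difference to be inflated, controls must also have a BAT at that visit. The size is unknown, and it is zero if the line is unused.

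Severity is minor to moderate: more than clerical, because it concerns how the effort-dependent primary outcome is prompted, but not a demonstrated bias.

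**What to change.** 1. Remove the closing script from the real-dog assessment in section 5.
2. State in sections 5 and 8: *Every BAT, at every visit and in every arm tested, uses the approach prompts of section 5 verbatim, with no comment on earlier sessions, progress or expected performance.*
3. Reword the opening of section 5, which has staff explain the measurement of progress, so that it agrees with item 2.
4. State whether a real-dog test takes place on the day of AR. If it does, list it and say that it uses the same script.
5. Correct the reference in section 8 from step 6 to step 5.

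These are changes of wording only, with the same staff, visits and sample size. They help under either reading: they prevent a cue if the line is in use, and remove an instruction that cannot be followed if it is not.

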- After the patient is comfortable and sitting close to the dog, we move the dog horizontally.
- We then add “Let’s see if you can touch its head or hold your hands close to it”. We calm and encourage the patient if needed until their SUDs go down.
- We move the dog to the far corner of the room. The dogs can perform actions such as sitting, barking, and jumping. We ask the patients to command “Sit!” to the dog and the dog sits. This way, the patient might feel a stronger sense of control over the events. Secondly, we ask the patients to command “Bark!” to the dog and the dog barks. Finally, we ask the patients to command “Jump!” to the dog and it jumps. In each turn, we ask the patients what the dogs are doing to engage their cognitive processing.
- Later, we ask the patients to call the dog near and sit. We control their SUDs and if it is below the threshold, we suggest the patients pet the dog while it is sitting.
- Finally, we say “I would put another dog here.” and put another breed of dog. “This dog will move a little bit here.” We ask the patients what the dogs are doing.
- We notify the patients that the dogs will move around and towards the person without prompts.
- In this room, we keep doing this until the SUDs get to the target SUD.
- Later, we say “Congratulations for doing this. Now, let’s go to the other room and try it there.”

b. The Second Room

- We explain to the patients that we will repeat the same exercises and start when they are ready.
- We start from the dog far away as in the first room. We ask the patients their SUDs. (Usually at that stage people state that they are comfortable).
- We bring the other dogs like it was done in the first room. We put all 3 different dogs here and there. If the patients are comfortable, we tell the patients that the dogs will walk around.
- When their SUD’s drop to 5, we say to the patients “Now, I will not give prompts about what the dogs will do. Is this all right for you?”
- Dogs will sit, walk, bark, and jump. Dogs first bark when they’re distant and they come closer and bark. During this stage, we will regularly monitor the SUDs.
- At the end, these dogs will be walking around, barking and jumping without prompt. After the patient is comfortable with the dogs’ sitting, barking, and jumping; we tell them “ We want you to feel comfortable by yourself and alone with these objects after

this intervention. So, if it is okay for you, I will leave the room and talk to you via a walky talky."

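### SUD steers and ends the AR session in one arm only and is also an unblinded between-group outcome, so differential reporting of the real-dog SUD needs to be guarded against

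*Combined protocol and SAP*

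**What the plan says.** **SUD inside the session (section 7, intervention arm only).** Staff ask for fear out of 10 and act on the answer: "Based on their level of fear we go on adjusting (Minimum to continue is 5/10". At the first movement step, "We keep repeating it until the participants' SUDs go down". A lower rating also moves the session forward: "When their SUDs decrease, we add the second dog". For the end of the first room the plan says "In this room, we keep doing this until the SUDs get to the target SUD", without giving the target a value; staff then say "Congratulations for doing this". The whole session finishes "When the participants are comfortable with their virtual phobic stimuli (SUD = 2) or their SUD's did not change for the last 10 minutes".

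**SUD at the real-dog test (section 5, repeated in section 8).** While skin conductance is recorded from a finger sensor, "participants will report how stressed they are (subjective unit of distress, SUD". Section 5 does not say to whom, in what form, at which moment of the test, or with which anchors. Section 8 applies the same real-dog measures at 1 week and 1 month.

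**SUD in the analysis (section 9).** The mixed models cover the primary approach test and the "secondary outcome measures (Specific Phobia Scale, Skin Conductance and Subjective Units of Distress". Section 9 does not say which SUD ratings are meant.

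**Knowledge of allocation.** Sections 4 and 5 both say that participants are told their group after the baseline test. No blinded assessor or private rating is described. Section 5 closes with a staff script telling participants that they have become comfortable with the dogs and that staff look forward to seeing how they do with the real one.

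**The concern.** A self-rating can be compared between randomised groups if both groups use the scale in the same way. Randomisation and the pre-allocation baseline secure that at the start. After baseline the arms diverge in two respects: how distressed people are, which is the effect of interest, and how much practice they have had in giving this particular number to staff who use it to run the session. The second is not a treatment effect on fear of dogs, yet it falls in the treated arm only.

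At stake is the meaning of a SUD difference. Someone who knows they were treated, has just been through a session steered by SUD, and is told that they are now comfortable may give a lower number at the real dog for the same distress. The mixed model cannot separate this from real improvement. Adjusting for baseline does not help, because the shift arises after baseline.

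**Working it through.** The plan states no sample size, SD, expected effect or significance level for SUD, so there is no figure to reproduce. The check is a comparison of the sections, followed by an illustration on assumed inputs.

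**1. Experience with the scale, by arm**

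| | AR arm | Control arm | Source |
|---|---|---|---|
| SUD at baseline real-dog test | yes | yes | section 5 |
| SUD asked and acted on in session | yes | no session | sections 4, 7 |
| Knows allocation after baseline | yes | yes | sections 4, 5 |
| Script about now being comfortable with the dogs | fits | does not fit | section 5 |
| SUD at later real-dog tests | yes | unclear: section 4 says controls are tested at baseline only | sections 4, 8, 9 |

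**2. How much of the session turns on SUD.** Section 7a has 21 bullets, of which 9 mention SUD. Three of those 9 tell staff to repeat or continue until SUD falls or reaches a target: the first horizontal movement, touching the dog, and the room exit. In section 7b, 4 of 10 bullets mention SUD: the opening rating, the move to unprompted dogs, the monitoring and the stop rule. SUD is therefore a frequent control signal, though not a gate at every step.

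**3. What the model estimates.** Let τ be the true effect on distress at the real dog and b the shift in reporting among treated participants after baseline. The expected group difference in post-baseline SUD, with or without baseline adjustment, is τ + b. SUD data alone cannot split the sum.

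**4. What a given b would do (illustration).** Set τ = 0 and use a two-sided 5% z-test of two means:

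- SE = SD × √(2/n)
- P(significant) = 1 − Φ(1.96 − b/SE) + Φ(−1.96 − b/SE)

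Assumed, not from the documents: n = 15 to 30 per arm, SD = 2.0 to 2.5 points, b = 0.5 to 1.5 points.

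For b = 1:
- n = 15, SD = 2.5: SE = 2.5 × √(2/15) = 0.913; b/SE = 1.095; P = 0.194 + 0.001 = 0.195.
- n = 30, SD = 2.0: SE = 2.0 × √(2/30) = 0.516; b/SE = 1.936; P = 0.491.

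| Assumed shift b | n = 15, SD 2.5 | n = 30, SD 2.0 |
|---|---|---|
| 0 | 5.0% | 5.0% |
| 0.5 | 8.5% | 16.2% |
| 1.0 | 19.5% | 49.1% |
| 1.5 | 37.6% | 82.8% |

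The table shows how sensitive the SUD comparison is to a shift of a given size. It is not an estimate of b.

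**The case against.** **Incentives.** A reader might infer that treated participants are trained and rewarded for giving low numbers. The text does not support that. During the session a lower rating often brings a harder step: the dog comes closer, another is added, prompts stop. The session also ends after 10 unchanged minutes at any level, so a low number is not needed to finish. The congratulation follows completion of the first room and does not praise a rating. The incentives are mixed, and the direction of any learned response style is not certain. This objection stands. What remains is unequal experience with the scale, open allocation and the expectancy script.

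**In-session ratings.** A reader might also infer that they will enter the outcome model, where steps that run until SUD falls would manufacture a decline. Sections 5 and 8 tie SUD to the real dog, and in-session ratings have no control counterpart, so the ordinary reading is that the outcome is the real-dog rating. Saying so in section 9 is a clarification. For the same reason, an in-session fall from 5 to 2 (3 points) measures no bias in the outcome. It concerns virtual dogs, and it needs the 5/10 rule to be an entry level, which the wording leaves open.

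**Who receives the rating.** Section 5 does not say that the real-dog SUD is told to staff. That is likely, but inferred.

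**Weight.** SUD is secondary. The primary approach test is a measured distance and skin conductance is physiological, so the double use of SUD does not touch them, although the approach test is also unblinded and verbally encouraged.

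**Conclusion.** The concern holds in limited form. The documents establish that SUD paces and ends a session given to one arm only, that SUD is also a between-group outcome, that participants know their group, and that nothing in the plan protects the real-dog rating from differential reporting. A lower real-dog SUD in the AR arm could therefore be partly a reporting difference.

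The size is unknown. The 20% to 49% for a 1-point shift rests entirely on the assumed sample size, SD and shift. The point affects the interpretation of one secondary outcome and does not undermine the primary one. It is worth acting on because the remedy is cheap.

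One matter comes first. If controls really are tested at baseline only, as section 4 says, there is no concurrent post-baseline control SUD, and the between-group model in section 9 has nothing to compare. The two sections must be reconciled.

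**What to change.** 1. **Sections 5 and 8, rating.** Give both arms the same written 0–10 anchors before baseline. At every real-dog test, have participants record SUD privately, unseen by the tester, at one defined point of the test, using the hand that does not carry the skin conductance sensor.
2. **Sections 5 and 8, script.** Use one neutral script in both arms before every real-dog test, in place of the line that presupposes the AR session.
3. **Section 9.** State that the SUD outcome is the rating at the real-dog tests only, and that ratings given during the AR session are reported descriptively as treatment delivery.
4. **Sections 4, 8 and 9.** Reconcile whether and when controls have real-dog tests after baseline.

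None of this changes how the session is run.

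**Cost.** A rating card, a short script and a few sentences; the rating and script changes need no extra staff or visits. If item 4 shows that control tests after baseline were not planned, adding them would cost visits, but the comparison in section 9 already requires them. There are three small downsides: a short pause to write, possible movement artefact in the skin conductance trace if the rating is not timed with care, and only partial protection. Private recording reduces pressure to please the tester but does not remove a response style learned during the session.

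### Section 9 names group as the only fixed factor and leaves visit, group-by-visit, baseline BAT and the primary contrast unspecified, although BAT is measured before randomisation and again at 1 week and 1 month

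*Combined protocol and SAP*

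**What the plan says.** Section 9 has two sentences. One names the software. The other gives the model: "Considering the groups as fixed factor, linear mixed models will be used to evaluate the effectiveness of the Augmented Reality Exposure Therapy", applied to BAT as primary outcome and to the Specific Phobia Scale, skin conductance and SUD as secondary outcomes. Neither section 9 nor any other section names a visit effect, a group-by-visit term, a role for baseline BAT, a random-effects structure, a primary time point or a contrast.

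The measurement schedule has to be put together from three sections:

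- **Section 4**, before describing random assignment: "After that the baseline measurements with the real dog will be taken".
- **Section 8**: "At 1 week and 1 month follow-ups, we contact the participants and invite them to the lab", with the real-dog test repeated.
- **End of section 5**: a script line, "see how you will do with the real dog", which follows on from the virtual dogs and so hints at a further test straight after the AR session. Section 8 does not list such a test.

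**The concern.** A pre-randomisation measurement and two follow-ups require decisions that the plan does not make. If both arms are followed, at least three analyses fit the text:

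- **A.** Group only, with baseline, 1-week and 1-month BAT all as outcomes.
- **B.** Group only, follow-up BAT as outcome, baseline unused.
- **C.** Group, visit and group-by-visit, with baseline rows as outcomes. The test could then be the group main effect, the 2-df interaction, or the change from baseline to the follow-up mean.

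These do not estimate the same quantity. Randomisation makes the expected baseline difference zero, so any analysis that averages baseline into the group effect shrinks it. B is unbiased but uses no baseline information. With no contrast named, the analyst can choose among them, and between 1 week and 1 month, after seeing the results. That weakens the primary test as a confirmatory one.

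**Working it through.** **Inputs from the documents.** One BAT before randomisation (section 4), two follow-ups (section 8), group as the named fixed factor (section 9). The plan states no sample size, power, alpha, effect, SD or correlation, so it has no figure to reproduce.

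**Dilution under A (algebra; needs only complete follow-up in both arms and a constant effect d).** Expected group differences at the three tests are 0, d and d. The group coefficient averages them: (0 + d + d)/3 = 2d/3. The group main effect in C, averaged over the three visits, is the same quantity. If the effect halves by 1 month, the average is (0 + d + d/2)/3 = d/2.

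**Illustrative power (all inputs assumed).** Unit variance at each test, d = 0.8 SD, n = 20 per arm, two-sided 5%, complete data. The correlation between follow-ups is ρ = 0.6 and that between baseline and follow-up is r = 0.6. The variance of the mean of two follow-ups is V = ρ + (1 − ρ)/2 = 0.6 + 0.2 = 0.8. Power uses the noncentral t with 38 df (37 for the adjusted analysis).

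| Analysis | Estimate | SE | Power |
|---|---|---|---|
| A: group only, baseline rows in | 2(0.8)/3 = 0.533 | √[2(1 + 4V + 4r)/(9n)] = √[2(6.6)/180] = 0.271 | 48% |
| B: follow-up only | 0.80 | √(2V/n) = √(1.6/20) = 0.283 | 79% |
| C: change contrast | 0.80 | √[2(V + 1 − 2r)/n] = √(1.2/20) = 0.245 | 89% |
| Baseline-adjusted follow-up mean | 0.80 | √[2(V − r²)/n] = √(0.88/20) = 0.210 | 96% |

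For the 2-df interaction in C, the noncentrality is (n/2)·Σ(m − m̄)²/(1 − ρ) with m = (0, 0.8, 0.8). The sum of squares is 0.4267, so the noncentrality is 10 × 0.4267/0.4 = 10.67. With 2 and 76 df, power is 83%.

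**Sensitivity to a common correlation (ρ = r).** From 0.3 to 0.7, power runs 61% to 45% for A, 86% to 76% for B, 57% to 92% for the interaction, 67% to 96% for change, and 91% to 98% for the adjusted analysis.

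**Sensitivity to a weaker baseline correlation.** Section 5 says "the participants who can touch the dog will be excluded from the study", which truncates baseline BAT and may lower r. Keeping ρ = 0.6:

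| r | A | B | Change | Adjusted | Adjusted minus B |
|---|---|---|---|---|---|
| 0.3 | 56% | 79% | 61% | 83% | 4 points |
| 0.2 | 60% | 79% | 55% | 81% | 2 points |

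The adjusted analysis comes out highest in every setting tried, but its margin over B can be small. The change contrast moves from above B to below it as r falls, so the ranking of the unadjusted options cannot be known in advance.

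**Visits that the model can cover.** Suppose the test hinted at in section 5 exists for treated participants only. A group-by-visit model over three post-baseline tests then has 2 × 3 = 6 cell means, but only 5 cells hold data, so its rank is 5 of 6. The model must be limited to tests that both arms attend.

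**The case against.** The strongest reply is that section 9 says group is a fixed factor, not the only one, and that choosing linear mixed models for a repeated test points to a model with time and interaction. That is fair. A reader might infer that the sponsor will fit the group-only model and report a diluted effect at roughly half the achievable power. The documents do not support that. They show that the model is unspecified, and dilution follows only under reading A or if the group main effect in C is the test. The reply does not close the gap, however. Even with visit and interaction fitted, the main effect, interaction and change contrast remain open, at 48%, 83% and 89% power on the same assumed inputs.

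The second reply is that every power figure rests on assumed inputs. This also stands. Only the 2/3 ratio follows from the design.

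A reader might also infer from section 4, "The control group will only be tested for baseline where the intervention group will receive Augmented Reality Exposure Therapy", that controls have no follow-up and that no treatment effect can be estimated. Read literally, that would be so. But the sentence may mean tested without being treated, and section 8 invites participants without limiting the arm. This is a separate question and carries no weight in the severity given here. The same holds for the reference in section 8, "We use the same measures and protocol as the 6th step, Real Dog", when the section so numbered is "6. Rooms for the Intervention". That is a clerical slip.

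**Conclusion.** The point holds as a gap in specification for the primary outcome, and it should be fixed. Confidence in the omission is high. Its practical size is uncertain, because no sample size, effect or correlation is documented. The literal model with baseline rows recovers 2/3 of a constant effect when both arms are fully followed. A follow-up-only analysis is unbiased, and its cost is lost precision alone, from 17 power points (79% against 96%) down to 2 to 4 in the settings above. The more lasting harm is that estimand and test can be selected after the data are known.

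**What to change.** Replace the model sentence in section 9 with, for example: *BAT at the post-baseline real-dog tests scheduled for both arms will be analysed by a linear mixed model with fixed effects for group, visit (categorical), group-by-visit and baseline BAT, and a participant random intercept.*

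Then name one primary contrast before any follow-up data are seen. It could be the group difference averaged over 1 week and 1 month, or a single visit of the sponsor's choice. All other contrasts become supportive. A model using all visits with baseline means constrained equal across arms is an acceptable alternative. Use the same form for skin conductance and SUD. Use it for the Specific Phobia Scale only if a post-baseline administration is scheduled, since the documents place it only at screening.

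Before finalising the text, state whether the section 5 script describes a scheduled test and in which arms, and correct the step reference in section 8.

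The cost is a few lines and commitment to one contrast. SPSS 26 MIXED fits the model, and baseline BAT is already collected. The fix presupposes follow-up BAT in controls. Sections 4 and 8 must be reconciled on that as a separate matter. If controls are not currently brought back, that means extra visits, and no model wording replaces them.
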